10.1 Primary study parameter(s)

Groin recurrence after SLN

The main study endpoint is the number of women who develop a groin recurrence within 24 months after a technically successful SLN procedure in which the SLN was free from tumour in recurrent vulvar cancer. The prognosis (survival) is related to failure, whether uni- or bilateral, therefore the primary endpoint relates to patients rather than groins.

Women should have a full groin node dissection in case of technical problems (SLN does not appear on the scintigraphy, or cannot be retrieved at surgery). So to calculate SLN failure the women with a groin failure after IFL will not be considered as failure of the SLN procedure.

Women that refuse to consent for standard treatment, i.e., an IFL when the SLN is not feasible (Group B2) will only be included in the analyses of the primary outcome if the SLN is retrieved.

This failure is calculated by:

Total number of women with groin recurrence in a groin after tumour-negative SLN procedure divided by the number of women with successful uni- or bilateral SLN procedure * 100%.

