5.1.1 Preoperative assessment

In accordance with current routine pre-operative imaging of the chest, abdomen and inguinal area is done by CT scan. In case of enlarged (> 10mm short axis) or suspicious nodes ultrasound of the groins with FNA should be performed to rule out metastatic involvement. When FNA is negative, patients can proceed to SLN procedure, the gynaecologic oncologist should in these cases be ensured that at least all (suspicious) enlarged nodes are removed.

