5.1.4 Surgical protocol

Treatment consists of wide local excision of the vulvar tumour or a vulvectomy in combination with SLN procedure. All groins with a SLN on imaging should be explored; also when previously IFL was performed at that site. When sentinel nodes in one or two groins cannot be identified an inguinofemoral lymphadenectomy at either one or two sides should be performed, depending on the location of the tumour and consent of the patient. (Figures 2, 3 and 4) When preoperative imaging showed any enlarged groin node (shortest axis > 8 mm) this node should be removed.

5.1.5 Histopathology:

Macroscopy: the number of lymph nodes received should be described, as well as the size and macroscopic aspects of the lymph nodes. The lymph node should be cut in 2-3 mm slices, perpendicular to the long axis and then all slices should be embedded (do not embed different lymph nodes in the same block).

Microscopy: one routine H/E section (four mu) should be cut of all blocks and two unstained sections (do not cut deep into the block). If the sections are tumour negative step sections, 3 levels/mm (one section per 500 micro meter), should be cut. For the three sections at each level, one is stained with H/E, one is to be used for immunohistochemistry (cytokeratin AE1/AE3), while one spare section is preserved in case of technical difficulties with the IHC (include the first level for IHC). Metastases are defined as clusters of tumour cells of any size detected on haematoxylin and eosin slides or at immunohistochemistry, or isolated tumour cells detected at immunohistochemistry. Anucleate keratin-positive structures are not considered positive. The diameter of the sentinel node metastasis and presence of extranodal growth will be recorded.

Pathologic ultra-staging will only be performed on sentinel nodes and not on non-sentinel nodes as identified in full lymphadenectomy specimens.

Reporting: number of sentinel nodes. Number of lymph nodes in lymphadenectomy specimen. Number of nodes with metastatic involvement. Size of lymph node metastasis. Extra nodal tumour growth.

5.1.6 Additional surgery:

In case of a positive SLN on histology a full IFL is advised. However, local protocol might advise postoperative radiotherapy under certain circumstances.

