8. METHODS

8.1 Study parameters/endpoints

8.1.1 Main study parameter/endpoint

The main study endpoint is the number of women who develop a groin recurrence within 24 months after a negative SLN procedure in 1st recurrent vulvar cancer. Clinical examination is done every 3 months, with an USS of the groin at 6 and 12 months. In case of suspicious findings FNA or histologic biopsy is performed.

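### The primary endpoint has no rule for a woman with a tumour-free sentinel node and a metastasis in another node removed at the same operation: as written she counts as SLN-negative

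*Protocol*

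**What the plan says.** - **Endpoint.** Protocol 10.1 counts women with a groin recurrence "within 24 months after a technically successful SLN procedure in which the SLN was free from tumour". Section 8.1.1 puts it differently: "the number of women who develop a groin recurrence within 24 months after a negative SLN procedure".
- **Rate.** In 10.1 the numerator is "Total number of women with groin recurrence in a groin after tumour-negative SLN procedure". The denominator is all women whose SLN procedure succeeded, on one side or both. Neither part mentions the histology of other removed nodes.
- **Recurrence after inguinofemoral lymphadenectomy (IFL).** Section 10.1 adds that "the women with a groin failure after IFL will not be considered as failure of the SLN procedure". This follows directly on the sentence about IFL after technical problems.
- **Other nodes removed.** Section 5.1.1 lets women with enlarged or suspicious nodes and negative fine-needle aspiration (FNA) go on to SLN, and the surgeon "should in these cases be ensured that at least all (suspicious) enlarged nodes are removed". Section 5.1.4 says: "When preoperative imaging showed any enlarged groin node (shortest axis > 8 mm) this node should be removed". Neither requires the enlarged node to be a sentinel node.
- **Stopping rule.** Appendix 1 counts groin recurrences among patients with a negative SLN. It accepts SLN with at most 7 failures in 150.
- **Where such a woman appears.** She can be identified only in the secondary rates for tumour-positive groins in 10.2.

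**The concern.** The trial asks whether a negative SLN can safely replace IFL. A tumour-free SLN beside a metastatic removed node in the groin shows directly, at surgery, that the SLN missed nodal disease. Under 10.1 that finding is not an event and does not take the woman out of the SLN-negative set. The Protocol Summary says that groin metastases found in the SLN procedure lead to further treatment by surgery and/or radiotherapy. If that treatment prevents recurrence, she contributes 24 event-free months to the rate for SLN alone, although she was known to be node-positive and was treated for it. The bias lowers the failure rate. With only 7 events allowed in 150, one or two women matter.

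**Working it through.** **1. Can the situation arise?** Yes. Sections 5.1.1 and 5.1.4 provide for removal of enlarged nodes, and 8.1.2 records sentinel nodes per groin separately from removed nodes per groin. Section 4.2 bars nodes > 10 mm, while 5.1.1 admits them after negative FNA. Nodes of 8–10 mm remain eligible on size under either section, and 5.1.4 has them removed.

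**2. How is she classified?** Section 4.4 has three categories among women undergoing SLN: positive SLN 11%, negative SLN 64%, unsuccessful 25%. The 11% is 0.75 × 14.5% = 10.9%, so every metastasis in a successful procedure is assumed to lie in the SLN. A tumour-free SLN with another positive node therefore falls under negative SLN. No section moves her.

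| Course after that finding | Status under 10.1 as written |
|---|---|
| Further groin treatment, no recurrence | Non-failure, in the denominator |
| Radiotherapy without IFL, then groin recurrence | Failure |
| IFL, then groin recurrence | Failure if the IFL sentence is confined to technical problems; not a failure if it is read broadly |

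**3. The plan's own figures.** Inputs from Appendix 1: N = 150, first look after 10 patients and then after each one, unacceptable failure rate 8%, target 3%, and Beta(0.2, 0.8) prior on the failure rate. The printed table stops the trial at 4 failures (n = 10–14), 5 (15–24), 6 (25–39), 7 (40–59) and 8 (60–150). An exact binomial recursion over these boundaries gives an acceptance probability of 0.0805 at 8% and 0.9160 at 3%, equal to the printed alpha and power.

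**4. Sensitivity.** Suppose the true rate of groin recurrence and surgically proven false-negative SLN combined is 8%, and k women per 150 fall in the second group and are not counted. The counted rate is 0.08 − k/150. Here k is an assumption, because the documents give no frequency.

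| k per 150 | Counted rate | P(accept SLN) |
|---|---|---|
| 0 | 8.00% | 0.0805 |
| 1 | 7.33% | 0.133 |
| 2 | 6.67% | 0.211 |
| 3 | 6.00% | 0.316 |
| 4 | 5.33% | 0.448 |

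For scale, 150/0.64 ≈ 234 procedures, and 234 × 0.11 ≈ 26 women with metastasis at a successful procedure. So k = 1 means about one in 26 of these has tumour only in a non-sentinel node.

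**5. Does exclusion alone cure it?** With these women outside the 150, the rate among the rest is (0.08 − m)/(1 − m), where m is their share.

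| m | P(accept), left in uncounted | P(accept), excluded |
|---|---|---|
| 0.5% | 11.8% | 11.5% |
| 1.0% | 16.8% | 16.0% |
| 1.5% | 23.4% | 22.0% |

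Exclusion removes little. Only counting these women, or showing their number, brings the information back.

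**6. Counting them as failures.** On top of a 3% recurrence rate, the rate is 0.03 + k/150. Acceptance falls from 0.916 (k = 0) to 0.812 (k = 1) and 0.674 (k = 2).

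**The case against.** - **She can still become a failure.** A reader might infer from the IFL sentence in 10.1 that no outcome can turn her into one. The text does not support that. The sentence is tied to IFL after a failed SLN procedure, 5.1.6 advises IFL only for a positive SLN, and a later groin recurrence meets the numerator. This objection stands.
- **Another reading exists.** Section 8.1.1 and the numerator in 10.1 speak of a negative or tumour-negative SLN procedure. Removal of enlarged nodes is part of that procedure, so she might already count as node-positive. This is possible, but the endpoint sentence in 10.1 names only the SLN, and the written denominator keeps her on either reading. The ambiguity is the reason for a rule.
- **The alpha figures change the endpoint.** The 3% and 8% benchmarks in 4.4 and Appendix 1 are groin recurrence rates, and a metastasis found and treated at surgery is not a recurrence. For recurrence alone, alpha stays at 0.0805. This stands: a reader should not infer that the design's type I error is miscalculated. The range in the working describes a combined definition of failure.
- **The group may be very small.** At 0.25 percentage points uncounted, acceptance is 9.8%, within the 10% limit. An enlarged node may also be the sentinel node. Both are fair.
- **The data are reported elsewhere.** Section 10.2 includes these women among tumour-positive groins, but there they are not shown as SLN misses beside the primary rate.

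**Conclusion.** The point holds as a gap in the endpoint definition. As 10.1 is written, a woman with a tumour-free SLN and a metastatic other removed node counts as SLN-negative and is a failure only if she later has a groin recurrence. Successful further treatment turns a proven false-negative SLN into a non-failure in the safety rate and in the stopping-rule count.

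The size is a sensitivity range. It assumes a true combined rate of 8% and k such women per 150 left uncounted. Acceptance is 8.0% with none, about 13% with one and about 21% with two, against the 10% limit in Appendix 1. The frequency is unknown and may be close to zero. The endpoint and the monitored count are fixed in the protocol, so the rule belongs there and should be made before data are seen.

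**What to change.** In 8.1.1, 10.1 and for the Appendix 1 count:

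1. Define a negative SLN procedure as one in which all nodes removed at the SLN operation, sentinel and non-sentinel, are tumour-free.
2. Classify women with a tumour-free SLN and another positive node as node-positive, outside both the numerator and the 150.
3. Report their number beside the primary rate as false-negative SLNs.
4. Prespecify a sensitivity analysis that counts them as failures against the 8% limit.

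Items 3 and 4 carry the correction. Item 2 alone leaves most of the effect in place.

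Separately, the passages on node size must be reconciled: > 8 mm in 5.1.4, and > 10 mm in 4.2, 4.3 and 5.1.1. So must the bar on enlarged nodes in 4.2 and their admission after negative FNA in 5.1.1. These passages determine which extra nodes are examined.

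**Cost.** A few sentences and one extra analysis. Nodes removed and nodes with metastases are already recorded (5.1.5, 8.1.2). A few women leave the denominator, so the reported rate may look slightly less favourable (7/150 = 4.67%; 7/148 = 4.73%). Filling the 150 needs about 1/0.618 ≈ 1.6 more inclusions for each woman displaced. The sensitivity analysis is stricter than the primary one, as the fall in acceptance at a 3% recurrence rate shows, so it should be read as supportive.

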4.4 Sample size calculation

Approximately 18% of women will have groin metastases at the moment of their first vulvar cancer recurrence. Of these, approximately 20% will be detected prior to surgery (based on imaging and FNA) and these women will not be offered a SLN procedure, but advised to undergo an IFL(s). They will be asked for the observational arm of the non SLN cohort. (See figure 2)

The remaining patients will be informed about the study, they can decide on standard IFL (group A) or refuse any surgery of the groin(s) (group C) In 75% of cases that undergo SLN (group B) it will be possible to retrieve the SLN. In approximately 14,5% of women undergoing a SLN procedure a tumour positive node will be present. It is not expected that the change of a successful SLN procedure relates to the presence or absence of a positive groin node. We expect to find a positive SLN in 11% of cases undergoing a SLN procedure, a negative SLN in 64%, and an unsuccessful procedure in 25%. This corresponds to respectively 10.5%, 61.8% and 24.1% of all included patients.

Percentage failure of SLN or IFL is known for neither procedure in the recurrent setting. In the primary setting groin recurrence after negative IFL and after negative SLN are both about 3%.

Sample size for V2SLN is calculated based on a conservatively estimated groin recurrence rate of 3%, with a maximum additional groin failure rate of SLN in local recurrent vulvar SCC of 5%. The sample size, considering an alpha of 0.10 and a beta of 0.20, is then calculated to be 150 patients with a first vulvar cancer recurrence undergoing a SLN procedure (group B) and a negative SLN (Figure 2) So, we expect that approximately 243 women with a 1st recurrence of vulvar cancer should be included in the study. Stopping rules with dynamic boundaries were constructed to guarantee the safety of the study by continuously monitoring the number of groin recurrences. See Appendix 1 for a detailed description of these stopping rules.

[figure not shown]

Figure 2 Flow diagram of calculation of sample size

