10.2 Secondary study parameters/endpoints

Groin recurrence after IFL

When enough patients agree on the standard arm (Group A) we might be able to calculate the number of women who develop a groin recurrence within 24 months after a negative IFL procedure in 1st recurrent vulvar cancer.

This failure is calculated by:

Total number of women with groin recurrence in a groin after negative IFL procedure divided by the number of women with uni- or bilateral IFL procedure * 100%.

Feasibility of the SLN procedure in recurrent vulvar cancer.

This is the success rate of detection and retrieval of the sentinel node, both related to the number of women, as well as number of groins in whom the proposed SLN surgery is successfully performed. (Group B1-B2)

Prior to surgery the surgeon has to state what groin surgery should be done; ipsi or bilateral groin treatment and what treatment should be done in case the SLN is not visible, or not found during surgery (see section 5.1.2.).

Feasibility is calculated:

- in relation to participants / patients:

Total number of women with successful SLN procedure(s) as per preoperative defined protocol, divided by the number of women that undergo the SLN procedure * 100%

- per groins:

Total number of groins with successful SLN procedure (as per preoperative defined protocol), divided by the number of groins that should be treated with the SLN procedure * 100%

Unexpected SLN's

This consists of SLN's in groins previously treated with IFL and or radiotherapy and SLN's found at unpredicted place, beyond the border of the regular IFL treatment. (Group B1-B2)

- *SLN in groins previously treated with IFL and or radiotherapy*
 - calculation of unexpected SLN's after previous IFL and or radiotherapy of the groin;

Total number of successful SLN's procedures in groins after previous IFL or radiotherapy of the groin, divided by total number of groins in whom a SLN was retrieved *100%.

- *SLN found at unpredicted places*

Total number of SLN's found at unpredicted places (outside the region of IFL), divided by total number of groins treated *100%.

- *Involvement of unexpected SLN's*

Total number of tumour positive unexpected SLN's, divided by total number of unexpected SLN's *100%.

Tumour positive SLN's

- as absolute number, and in relation to participants / patients:

Total number of women with uni or bilateral tumour positive SLNs, divided by the number of women with a successful SLN procedure * 100%.

- per groins:

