Total number of groins with tumour positive SLNs, divided by the number of groins with successful SLN procedure * 100%.

Tumour positive groins

- in relation to participants / patients with groin surgery (pathology only):

Total number of women with uni or bilateral tumour positive lymph nodes, retrieved either by SLN or by IFL, divided by the number of women that underwent groin surgery * 100% (including women included in the non-SLN cohort, excluding women that did not have groin surgery in groups B2 C).

- in relation to participants / patients with first vulvar cancer recurrence:

Total number of women with uni or bilateral tumour positive lymph nodes, retrieved either by SLN or by IFL, and all women experiencing a groin recurrence during 24 month follow up, divided by the number of women included in the current study * 100% (including women included in the non-SLN cohort, and women that did not have groin surgery in group B2 and C).

- per groin:

Total number of tumour positive nodes divided by the number of groins treated *100%.

Outcome quality of life

QoL measurements will be done at baseline and 6, and 12 months after surgery.

Linear description and comparison between standard treated and study arm treated patients will be performed. (Groups non SLN cohort, and A - C)

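### The section 10.1 failure formula divides recurrences after a tumour-negative SLN by all successful SLN procedures, so the primary rate reads about 15% (relative) too low

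*Protocol*

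**What the plan says.** Protocol section 10.1 sets the primary endpoint as groin recurrence "within 24 months after a technically successful SLN procedure in which the SLN was free from tumour". The formula that follows has the numerator "Total number of women with groin recurrence in a groin after tumour-negative SLN procedure" and the denominator "divided by the number of women with successful uni- or bilateral SLN procedure * 100". The tumour-free condition is in the endpoint sentence and the numerator but not in the denominator.

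Elsewhere the protocol keeps to SLN-negative women:
- Section 8.1.1 defines the main endpoint after a negative SLN procedure.
- Section 4.4 sizes the study at 150 women with a negative SLN.
- The caption of Figure 3 in Appendix 1 plots recurrences against patients with a negative SLN.

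Section 10.2 shows what a successful procedure is. Feasibility is detection and retrieval of the node, and the SLN-positivity rate is "Total number of women with uni or bilateral tumour positive SLNs, divided by the number of women with a successful SLN procedure".

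Two other formulas in section 10.2 are relevant. The IFL failure rate takes recurrences after a negative IFL "divided by the number of women with uni- or bilateral IFL procedure * 100". The per-groin rate of tumour-positive groins is "Total number of tumour positive nodes divided by the number of groins treated *100".

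**The concern.** A woman with a tumour-positive SLN is a technical success, so she enters the denominator. She is then advised IFL, or may have radiotherapy under local protocol (section 5.1.6), and her positive groin cannot supply a numerator event. Each such woman lowers the reported failure rate without having been exposed to the risk being measured, which is recurrence in a groin left undissected because its SLN was negative.

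The primary objective is the safety of replacing IFL by SLN. The acceptability limits, a 3% target and an 8% maximum, are set for SLN-negative women. A rate computed over a wider group is not on the same scale as those limits, and it errs in the direction that favours the new procedure.

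**Working it through.** **Inputs.** Section 4.4: "We expect to find a positive SLN in 11% of cases undergoing a SLN procedure, a negative SLN in 64" per cent, with 25% unsuccessful; as shares of all included patients, 10.5%, 61.8% and 24.1%; 150 SLN-negative women; 243 included. Appendix 1: success rates 0.92 and 0.97 (failure 8% and 3%), error limits 0.10 and 0.10, attained alpha 0.0805 and beta 0.0840.

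**Reproducing the plan's own figures.**
- Inclusion: 150 / 0.618 = 242.7, that is 243. This confirms that the 150 are SLN-negative women.
- Design: an exact binomial recursion through the printed boundaries was run from patient 10 to patient 150. It stops at 4 failures for n = 10–14, 5 for 15–24, 6 for 25–39, 7 for 40–59 and 8 for 60–150. It gives alpha 0.0805, power 0.9160 and expected sample sizes 93.48 and 147.74, all as printed.

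**What the formula returns.** If SLN-positive women contribute no events, then

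formula rate = true rate × negative / (negative + positive).

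- Planned split: 64 / (64 + 11) = 64/75 = 0.853, a relative understatement of 11/75 = 14.7%.
- All-patient figures: 61.8 / (61.8 + 10.5) = 0.855, or 14.5%.
- Rebuilt from 18% node-positive with 20% of these found before surgery: 0.18 × 0.80 / 0.964 = 14.9% positive, so 14.9%.

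| Situation | SLN-negative denominator | Formula in 10.1 |
|---|---|---|
| True rate 8% | 8.0% | 0.08 × 0.853 = 6.8% |
| True rate 3% | 3.0% | 0.03 × 0.853 = 2.6% |
| 7 recurrences, 150 SLN-negative women | 7/150 = 4.7% | 7/175.8 = 4.0% |

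Here 175.8 = 150 / 0.853 is the expected number of successful procedures when 150 are negative. Seven is the most recurrences with which the trial can complete, because 8 stops it from n = 60 on.

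**Does the error reach the stopping rule?** As written, no. The rule is a count boundary on SLN-negative women, and the section 10.1 percentage does not enter it. As a hypothetical only, suppose the same boundaries were run on 150 successful procedures, about 150 × 0.853 = 128 of them negative. The chance of accepting SLN at a true 8% failure rate would then rise from 0.080 to 0.189. Row 128 of the printed null table, 0.1872, agrees. Taking the SLN-positive share as anywhere from 10% to 20% gives 0.147 to 0.249.

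**The case against.** The best defence is that the intended population is clear. The endpoint sentence, section 8.1.1, the sample size and the stopping-rule figure all name SLN-negative women, and an analyst could report both denominators. The absolute effect is also modest: at most 0.7 percentage points in a trial that completes with 150 SLN-negative women. The 8%-read-as-6.8% case is an expectation at a rate where the design stops early with probability 0.9162. All of this stands and limits the harm. It does not rescue the formula, which is explicit, contradicts the sentence it implements, and is what an analyst following the protocol would compute. Reading successful as tumour-negative is not open, because section 10.2 counts positive SLNs among the successful procedures.

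Two stronger readings are tempting and are not supported:
- A reader might infer that the type I error is inflated to about 0.19. Section 4.4 and Appendix 1 run the rule on SLN-negative women, so alpha stays at 0.0805. Section 12.5 does describe the end of the study in terms of successfully treated patients (125 of them), but it does not redefine the population of the stopping rule.
- A reader might infer that SLN-positive women can never enter the numerator. The numerator refers to a groin, so a woman with one positive and one negative groin counts if the negative groin recurs. The 14.7% is therefore an upper figure for the planned split, and marginally smaller if such events occur.

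The IFL rate is conditional on enough women choosing IFL, and the nodes-per-groin rate is a separate descriptive measure. Neither adds to the weight of the main point.

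**Conclusion.** The section 10.1 formula is wrong as written. It understates the groin failure rate among SLN-negative women by about 14.7% in relative terms (14.5% to 14.9% across the protocol's own figures). That is 1.2 percentage points at a true 8%, 0.4 at a true 3%, and 0.7 for 7 recurrences among 150 SLN-negative women. The size rests on the planned 11%/64% split and on SLN-positive women contributing no events; the realised size will follow the observed share of positive SLNs. What is affected is the reported primary estimate and its comparison with the 3% and 8% limits. The sample size, the stopping boundaries and their error rates are unaffected as the protocol states them.

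**What to change.** In section 10.1, define one population for both numerator and denominator: women with a technically successful SLN procedure in whom all retrieved SLNs were tumour-negative. Women with one positive and one negative groin then leave both parts and are reported separately. This agrees with section 10.2, which already classes a woman with a positive SLN on either side as SLN-positive. Changing the denominator alone would not be enough, since such a woman could then appear in the numerator but not in the denominator.

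Make the same correction to the IFL failure rate in section 10.2: women with a tumour-negative IFL in both parts.

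As a separate minor correction, the per-groin rate in section 10.2 should count groins with at least one tumour-positive node. One groin can hold several positive nodes, so nodes divided by groins is not a proportion and can exceed 100%.

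The cost is a wording amendment and the decision on mixed-result women. No patients, visits or data are added. On the planned split the reported primary rate rises by a factor of 75/64 = 1.17.
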